4.4 Statistical Plan

4.4.1 Sample Size Determination

The desired sample size – 54 subjects – was calculated employing a baseline blood testing rate of 60% in the control group, a power of 80%, type I error of 5%, and a minimally clinically important difference of 40% in the proportion of children who experience **the primary outcome** (i.e. have any blood testing performed within 72 hours). Thus, we hypothesize that 20% of children in the intervention arm will have blood testing performed. The estimation of children having any blood testing performed within 72 hours (i.e. meeting our primary outcome measure) is based upon data from the APPETITE study (currently 62% among children with hematochezia). Based on previous experience we estimate that 10% of subjects will be lost to follow-up; hence the final sample size is 60 in total. Sample size requirements will be recalculated after the enrollment of 30 children. Based on the enrollment into APPETITE of 935 children at ACH since April 2015 and the presence of hematochezia in approximately 5% of children (23/506 on whom these data were collected), we anticipate that through the identification of potential participants outside of research coverage hours, we should be able to recruit our cohort over the span of 12 months.

4.4.2 Statistical Methods

All analyses will be undertaken by the intention-to-treat (ITT) principle. Patients who drop out or crossover will be followed and included in the ITT analysis. All statistical tests will be two-sided. Baseline characteristics will be analyzed and compared. Sensitivity analyses will be performed to assess the possibility and consequences of non-random loss to follow-up. The proportion of children who have any blood testing performed within 72 hours of randomization, **the primary outcome**, will be analyzed by comparing proportions utilizing a Fisher’s Exact test. We will use an alpha level of 0.05 for statistical testing.

The overall significance level for statistical tests on the **secondary outcomes** will be set at 0.05 with adjustment for multiple comparisons performed using a Bonferroni correction.

Ethics ID: REB17-1916

Title: Improvements Through the Use of a Rapid Multiplex PCR Enteric Pathogen Detection Kit in Children with Hematochezia

PI: [name]

Version 5.0 – May 16, 2018

Previous REB Approved Version Date: January 12, 2018

Dichotomous outcomes to be evaluated include 1) intravenous rehydration, 2) ED revisits, 3) any healthcare revisits and 4) hospitalization within the subsequent 14 days. Clinical outcomes will also include development of 5) HUS, 6) Kidney Disease Improving Global Outcomes Stage 2 or 3 creatinine based acute kidney injury,³¹ 7) antibiotic use, and 8) diagnostic imaging.

Recursive partitioning analysis will be employed to identify clinical features that select candidates for BioFire testing that maximize specificity and sensitivity to identify STEC patients. Analyses will be performed blinded to allocation assignment.

5 Adverse Event Reporting

Anticipated disease outcomes (listed below) are sought to be a natural continuation of the disease and as a result, the following will not be reported to REB:

1. IV insertion
2. Blood tests
3. Abdominal pain
4. Fever
5. Vomiting
6. Diarrhea
7. Bloody stool
8. Dialysis
9. Renal abnormalities
10. Hematological abnormalities
11. Biochemical abnormalities
12. Transfusions
13. Seizures
14. Hospital admissions
15. Other known complications of STEC infection

6 Data Handling and Record Keeping

Patients will be assessed and treated by ED staff without any regard to this study. Stool specimen testing will continue as per standard of care. Once the inclusion criteria are confirmed and parental consent is obtained (and child assent when appropriate) an enrollment ID number will be assigned. Recruitment and specimen collection will commence after ethics approval is obtained.

We may need to contact subjects in the future regarding research questions which may be discovered from the data collected in this study. Select administrative data may also be accessed to allow linkages beyond study collected outcomes.

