1. If use of the **BioFire FilmArray**, a rapid, multi-analyte enteric pathogen detection device, reduces resource utilization in a pediatric ED when employed on children with bloody diarrhea. **We hypothesize that use of the test combined with behavioural changes by physicians will reduce the use of baseline blood tests, the administration of intravenous fluids and future health-care resource use** (children are often brought back for repeat blood tests and fluids while awaiting culture results).
2. If satisfaction is higher in individuals randomized to testing with the BioFire FilmArray arm compared with children in the standard care arm.

Potential child health improvements:

1. **Children with STEC infection will be rapidly identified:** We have shown that in the 2014 STEC outbreak in Alberta, the median time from initial health care presentation to stool sample collection was 7 hours (IQR 2, 28) and to sample receipt at the laboratory was 33 hours (IQR 18, 42). Even more concerning is that the time from initial health care encounter to positive culture was 120 (IQR 86, 205) hours. By collecting rectal swabs at the point of care we will initiate specimen processing an average of 30 hours earlier. By employing the BioFire FilmArray we will reduce stool processing time by over 80 hours.
2. **Children with STEC infection will have dehydration reversed rapidly and they will be closely monitored:** Following the rapid identification of children with STEC infection, all such children will be managed in accordance with a protocol developed by the APPETITE team for Alberta Health Services (<http://www.albertahealthservices.ca/assets/info/hp/diseases/if-hp-dis-ecoli-stec.pdf>), which includes the performance and monitoring of serum biochemistry and hematologic profiles and the prevention of dehydration. It is believed that the early administration of intravascular volume expansion has the potential to reduce the morbidity of HUS in affected children.^{6,7}

Ethics ID: REB17-1916

Title: Improvements Through the Use of a Rapid Multiplex PCR Enteric Pathogen Detection Kit in Children with Hematochezia

PI: [name]

Version 5.0 – May 16, 2018

Previous REB Approved Version Date: January 12, 2018

Page 6 of 19

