4.3 Study Procedures

Children randomized to the standard of care arm and the BioFire FilmArray arm will have clinical data collected:

- 1) Day 0 – ED enrollment visit (In person): At the initial screening visit, the research assistant or research nurse will explain the nature of the research project to the family. Informed consent, and assent if applicable, will be obtained. A detailed medical history will be documented to ensure the subject's eligibility for inclusion in the study. Parents will be asked to participate in a standardized 10 minute survey administered by study personnel. The survey will collect descriptive data regarding current medical history (i.e. diarrhea – frequency/duration/blood; vomiting – frequency/duration; fever; pain; health care use; treatment required/procedures performed), previous medical history (i.e. investigations), household pets, and childcare arrangements. The information will be entered in our electronic data capture system (REDCap), and all charts will be reviewed in the ED.
 - a. Specimen Collection: Subjects who qualify for the study will have a stool sample collected, or a rectal swab specimen will be collected if stool is not available for either cohort (Standard Care and BioFire). Children who have a rectal swab collected at this visit will be requested to submit a stool specimen for culture after the ED visit.
 - b. Letter to parents: Only subjects randomized to the BioFire FilmArray arm will be given a letter. The letter outlines their assignment to the BioFire arm and what that means.
- 2) Day 14 Follow-Up: Data regarding ongoing symptoms, any hospital visits/admissions and locations of the respective hospital visits/admissions, testing and procedures conducted as well as parental satisfaction of the experience at the ED will be collected. Parental reports will act as source documentation for data that is related to any additional healthcare visits as well as care in relation to the respective visits not associated with the Alberta Children's Hospital. At the initial point of contact, we will collect the following data: home, cell, work and alternate telephone numbers. For phone follow-up, we will call all numbers provided at least once daily (maximum 5 attempts). Study participants will not be identified by name on study document except the Contact Sheet.

Ethics ID: REB17-1916

Title: Improvements Through the Use of a Rapid Multiplex PCR Enteric Pathogen Detection Kit in Children with Hematochezia

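### The primary Fisher's exact test is valid and adequately powered, but a stratified exact test using one pre-randomization factor could gain power from the same 60 children

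*Combined protocol and SAP*

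**What the plan says.** Section 4.4.2 states that the primary outcome "will be analyzed by comparing proportions utilizing a Fisher" exact test. It adds "All statistical tests will be two-sided" and "We will use an alpha level of 0.05 for statistical testing". Baseline characteristics are to be described and compared, but no stratified or adjusted primary analysis is given. Section 4.1 has a REDCap tool randomize the children and names no stratification factor.

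Section 4.4.1 sizes the trial at 54 evaluable children and 60 enrolled after 10% loss. It uses "a baseline blood testing rate of 60% in the control group", "a power of 80%, type I error of 5"%, and the statement that "we hypothesize that 20% of children in the intervention arm will have blood testing performed". It also plans to recalculate the sample size after 30 children.

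Section 4.3 describes a Day 0 survey in both arms. Among its items are "fever; pain; health care use; treatment required/procedures performed". It does not say whether the survey comes before or after randomization.

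**The concern.** With about 27 to 30 children per arm, one unadjusted 2x2 table leaves two things on the table. If some baseline fact predicts who gets blood drawn, ignoring it costs power, and a chance imbalance in it can move the estimate. Fisher's test is also conservative at this size: its actual type I error is about 2.5%, half the nominal 5%.

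The margin is thin. The planned 54 is the smallest equal-arm size that reaches 80% under Fisher, and that rests on a 40-point effect. If the true intervention rate were 30% instead of 20%, Fisher's power would be about 48% at 27 per arm and 56% at 30. Extra power from data already being collected is therefore worth having.

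**Working it through.** **Inputs from the documents.** Control rate 60%, intervention rate 20%, two-sided alpha 0.05, 54 evaluable and 60 enrolled (sections 4.4.1 and 4.4.2).

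**Assumptions.** Allocation is 1:1. This is not stated, but section 7 budgets 30 tests for 60 children. The stratifying factor is binary with prevalence 10%, 30% or 50% and a within-arm odds ratio for blood testing of 1 to 10. The overall rates stay at 60% and 20%, and the treatment odds ratio is the same in both strata. None of the factor's properties is in the documents.

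**Step 1: the plan's own figure.** Fisher's power is the sum, over all pairs (x, y) with Fisher p ≤ 0.05, of Bin(x; n, 0.6) × Bin(y; n, 0.2). Full enumeration gives 79.93% at 26 per arm, 80.24% at 27 and 85.08% at 30. So 2 × 27 = 54 is the smallest size reaching 80%, and 54 / 0.9 = 60. The plan's figure reproduces.

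**Step 2: the stratified test.** In stratum k the number of control children tested, given the margins, is hypergeometric under the null. The statistic is the sum over the two strata, and its null distribution is the convolution of the two hypergeometrics. The two-sided p-value adds the probabilities of all totals no more likely than the one observed.

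Example of a scenario: prevalence 50% and odds ratio 5 give control rates of 42% and 78% (mean 60%) and intervention rates of 8% and 32% (mean 20%).

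Simulated power (20,000 to 40,000 trials per scenario, stratum counts left random):

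| Odds ratio | 27/arm, prev. 50% | 27/arm, prev. 10% | 30/arm, prev. 50% | 30/arm, prev. 10% |
|---|---|---|---|---|
| Fisher | 80.2% | 80.2% | 85.1% | 85.1% |
| 1 | 82.8% | 82.4% | 86.7% | 86.5% |
| 3 | 85.5% | 84.2% | 88.7% | 87.3% |
| 5 | 87.5% | 84.7% | 90.8% | 88.2% |
| 10 | 90.7% | 86.3% | 93.6% | 89.6% |

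Prevalence 30% is within about 1 point of the 50% columns. Type I error of the stratified test was 3.2% to 3.6% across the null scenarios, against 2.4% to 2.8% for Fisher.

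In sample-size terms at 50% prevalence, Fisher needs 32 per arm (88.7%, 64 children) to match odds ratio 3 with 60 children. It needs about 34 per arm (90.7%, 68 children) to match odds ratio 5.

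**Step 3: how much of the gain is prognosis?** With odds ratio 1 the factor carries no information, yet power still rises by 82.8 − 80.2 = 2.6 points at 27 per arm and 86.7 − 85.1 = 1.6 points at 30. That part comes from a less coarse reference distribution. Boschloo's unconditional exact test, with no covariate, gives 85.5% at 27 per arm (maximum type I error 4.5%) and 89.9% at 30 per arm (4.7%). So odds ratio 3 gains no more than Boschloo. Odds ratio 5 at prevalence 50% beats it by 2.0 points (27 per arm) and 0.9 points (30 per arm). At prevalence 10%, even odds ratio 10 only roughly matches it.

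**Step 4: a smaller true effect.** With a 30% intervention rate, 30 per arm and prevalence 50%, Fisher has about 56%. The stratified test has 62% at odds ratio 3 and 64% at odds ratio 5.

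**The case against.** The strongest reply is that nothing is broken. Fisher's test is prespecified, valid and matched to the sample size. If chart review yields the outcome for all 60 children, power is already 85.1%, and a recalculation after 30 children is planned. An unadjusted primary test is a legitimate choice in a trial this small. All of this stands, and it is why the point is an improvement and not an error.

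A reader might infer from section 2, where "children are often brought back for repeat blood tests and fluids while awaiting culture results", that an earlier visit is a documented predictor of testing. It is not. That remark explains future resource use, meaning children returning after the ED visit. It does not say that a visit before enrolment changes the chance of a blood test within 72 hours, and even the direction is unclear. No passage links any baseline factor to the outcome.

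A reader might also infer that the whole gain comes from baseline information. Step 3 shows otherwise.

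Nor is the gain guaranteed. If the strata are exactly balanced across arms, for example by stratified randomization, it shrinks at 30 per arm to about 0, 1, 3 and 5 points for odds ratios 1, 3, 5 and 10. At 28 per arm a noise factor then cost 0.8 points. If the factor acts only in one arm, or in opposite directions, the gain is about 2 to 5 points.

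Finally, it is tempting to use any Day 0 item. Treatment required and procedures performed could include care given after allocation, and section 4.3 does not place the survey before randomization. Such items would undermine the test's error control.

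**Conclusion.** The point holds as an efficiency improvement to a valid analysis. For odds ratios of 1 to 10 and prevalence of 10-50%, the stratified exact test raises power from 80% to about 82-91% at 27 per arm and from 85% to about 87-94% at 30 per arm, with type I error of 3-4%. The upper ends need a strong factor that is also fairly common. Below an odds ratio of about 5, Boschloo's test without a covariate does as well or better on power, although it does nothing about chance imbalance. The result rests on 1:1 allocation, on stratum counts left to chance, and on a prognostic strength the documents do not supply. The reading that the plan is underpowered or uses an invalid test is not supported.

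**What to change.** In section 4.4.2:

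1. Make the primary test the exact conditional Cochran-Mantel-Haenszel test, two-sided at 0.05, stratified by one named binary factor.
2. Fix the factor before any outcome data are seen. Require that it describes a fact existing before randomization and is recorded before the arm is known. Candidates are any health-care visit for this illness before the enrolment visit (yes/no), or an eligibility fact such as age group. Exclude treatment required and procedures performed. Making the item a required field before REDCap releases the allocation avoids missing values.
3. Report the Mantel-Haenszel risk difference and name the method for its 95% CI. State that a large-sample interval is not exact and may disagree with the test when strata are sparse.
4. Keep Fisher's test as a supportive analysis, and say which test the recalculation after 30 children will use.

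If the team has no factor it believes to be strongly prognostic, Boschloo's test is the simpler alternative for power.

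The cost is protocol wording, one required field before randomization and a short piece of code, with no extra children or visits. The downside is that the factor must be chosen in advance without evidence in the documents, and the gain may be small if it is weakly prognostic.

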1. Do individuals randomized to testing with the BioFire FilmArray undergo fewer procedures (i.e. blood tests, intravenous fluids) and repeat healthcare visits compared with children in the standard care arm?
2. Are patient and caregiver satisfaction higher in individuals randomized to testing with the BioFire FilmArray arm compared with children in the standard care arm?

Ethics ID: REB17-1916

Title: Improvements Through the Use of a Rapid Multiplex PCR Enteric Pathogen Detection Kit in Children with Hematochezia

PI: [name]

Version 5.0 – May 16, 2018

Previous REB Approved Version Date: January 12, 2018

Page 7 of 19

Primary Objective

1. To determine if **use of the BioFire FilmArray in children with hematochezia results in a reduction in resource utilization.** Primary outcome – any blood tests (dichotomous with sub-analysis by specific blood tests); secondary – intravenous fluid administration, ED encounters.

Secondary Objectives

1. To quantify clinical outcomes – development of HUS, acute kidney injury, need for renal replacement therapy, turnaround time from BioFire result relative to stool culture result.
2. To determine if use of the BioFire FilmArray is associated with greater family satisfaction with care.
3. To determine testing criteria to optimize the clinical improvement emerging from use of the BioFire FilmArray (i.e. predictors of bacterial etiology).

4 Patients and Methods

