4.1.1 Outcome Variables

We will track the following on all participants:

Primary Outcome Measure:

1. Blood test performance, any blood testing performed within 72 hours of randomization;

Secondary Outcome Measures:

2. Intravenous fluid administration, children administered IV fluids identified by chart review;
3. Total physician visits (ED and non-ED), children visiting additional health-care practitioners identified by chart review;
4. ED length of stay, ED length of stay during enrollment visit determined by chart review;
5. Antibiotic use, antibiotic use identified by chart review;
6. Hospital and intensive care unit admission, hospitalization identified by chart review;
7. Diagnostic imaging performed, diagnostic imaging performed identified by chart review;
8. HUS, children with HUS identified by chart review;

Ethics ID: REB17-1916

Title: Improvements Through the Use of a Rapid Multiplex PCR Enteric Pathogen Detection Kit in Children with Hematochezia

PI: [name]

Version 5.0 – May 16, 2018

Previous REB Approved Version Date: January 12, 2018

Page 10 of 19

9. Acute kidney injury, based on chart review in accordance with KDIGO guidelines;
10. Need for renal replacement therapy, renal replacement therapy identified by chart review; and
11. Caregiver and patient satisfaction, satisfaction of care received during ED visit answered in Day 14 follow-up form on a Likert scale

4.2 *Subject Selection and Withdrawal*

4.2.1 *Inclusion Criteria*

Eligible children will:

1. Be aged 6 months – 17.99 years of age
2. Have ≥ 3 episodes of diarrhea within the preceding 24 hours and have blood identified in the stool (by physician, nurse or parent)

4.2.2 *Exclusion Criteria*

Children with any of the following will not be eligible:

1. Previously enrolled in the study
2. Unavailable for Day 14 follow-up
3. Currently (most recent complete blood count) known to be neutropenic (Neutrophils <1000), or at high-risk of being neutropenic (receiving chemotherapy) at present
4. Known to be STEC positive (stool culture, PCT, or toxin)
5. Language barrier that prevents the ability to obtain informed consent and assent (when appropriate)

4.2.3 *Study Withdrawal and Discontinuation*

Subjects will be withdrawn if:

1. If it is deemed by the investigator or treating physician that the child's health may be jeopardized by continued participation in the study (prior to sample collection)

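### Holm's step-down procedure on the eight outcomes numbered in section 4.4.2 would keep the same 0.05 bound as the planned Bonferroni correction and never reject less; the gain is nil to modest and almost free

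*Combined protocol and SAP*

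**What the plan says.** Section 4.4.2 (Statistical Methods) sets an overall level of 0.05 for the secondary outcomes, two-sided, with "adjustment for multiple comparisons performed using a Bonferroni correction". It states neither a divisor nor a per-test level. The next paragraph numbers eight outcomes: 1) intravenous rehydration, 2) ED revisits, 3) any healthcare revisits, 4) hospitalization, 5) HUS, 6) stage 2 or 3 acute kidney injury, 7) antibiotic use and 8) diagnostic imaging. HUS enters with the words "Clinical outcomes will also include development of 5) HUS".

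Section 4.1.1 has a longer list of ten secondary outcomes under "We will track the following on all participants". ED length of stay, renal replacement therapy and satisfaction are on that list but not among the eight.

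Two of the eight carry a stated hypothesis or objective. Section 2 expects the test to reduce "the administration of intravenous fluids and future health-care resource use", and the primary objective in section 3 names as secondary measures "intravenous fluid administration, ED encounters". Fisher's exact test is named for the primary outcome only.

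**The concern.** Bonferroni compares every p-value with 0.05/8, even after some null hypotheses have been rejected. Holm relaxes the threshold after each rejection and still holds the family-wise error rate at 0.05 under any dependence between outcomes. Using Bonferroni therefore gives up some power for no gain in error control. The trial is sized on its primary outcome alone, so power for intravenous fluids and return visits is already limited, and those are the outcomes where the loss would matter.

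**Working it through.** **Inputs from the documents.** Overall secondary level 0.05, two-sided, eight numbered outcomes (4.4.2). Primary outcome 60% v 20%, 80% power, 54 children, 60 after 10% loss (4.4.1). About 10% of eligible children with STEC (section 2). About 15% of infected children developing HUS, stated for O157 (section 1).

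**Assumptions.** Allocation is 1:1, which fits the budget for 30 tests. Fisher tests are used for the secondaries. The documents give no secondary rates, so 60% v 20% (borrowed from the primary), 50% v 20% and 30% v 10% are tried. The simulations for the first two pairs gave six outcomes the stated control rate, HUS 1.5% and acute kidney injury 5% in both arms, with latent correlation 0.3.

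**The plan's own figures.** Exact Fisher power for 60% v 20% at 27 per arm and 0.05 is 80.2%, and 54/0.9 = 60, so the sample size reproduces. For the secondaries, 8 × 0.00625 = 0.05, so Bonferroni on eight keeps the stated bound.

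**Thresholds.** Bonferroni uses 0.05/8 = 0.00625 for all eight. Holm orders the p-values and compares the i-th smallest with 0.05/(8 − i + 1), stopping at the first failure: 0.00625, 0.00714, 0.00833, 0.01, 0.0125, 0.01667, 0.025, 0.05. No threshold is below 0.00625, so no Bonferroni rejection can be lost. For illustration, take 0.0046 and 0.0068 as the two smallest p-values. Bonferroni rejects the first only. Holm also rejects the second, because 0.0068 < 0.00714.

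**Error rate.** In 200,000 simulated sets of normal test statistics per setting, no Bonferroni rejection was lost under Holm. The highest family-wise error was 0.0485 for both methods.

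**Gain in mean power per real effect, in percentage points, Holm on eight against Bonferroni on eight:**

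| Assumed rates | Real effects | 27 per arm | 30 per arm |
|---|---|---|---|
| 60% v 20% | 1 | 0 | 0 |
| 60% v 20% | 2 | 0.4 | 0 |
| 60% v 20% | 3 | 0.6 | 1.8 |
| 60% v 20% | 6 | 3.9 | 6.9 |

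With three real effects the gain is about 0.6 to 0.8 at 50% v 20% and 0 to 0.2 at 30% v 10%. At 30% v 10% it stays at or below about 0.4 even with six. Single-test exact power at 0.05/8 is 54.6% (27 per arm) and 59.9% (30 per arm) at 60% v 20%, and 24.7% and 30.1% at 50% v 20%.

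The gain is small because the smallest p-value must still pass 0.05/8. Fisher's test is also discrete: at 30 per arm, power at 60% v 20% is 59.9% at both 0.05/8 and 0.05/7, so Holm's second step adds almost nothing there.

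**HUS.** Expected cases are 60 × 0.10 × 0.15 = 0.9, applying the O157 risk to all STEC. The chance of no case is (1 − 0.015)^60 = 40%. Under Fisher, 7 v 0 gives p = 0.0100 at 27 per arm and 0.0105 at 30, both above 0.00625. A split of 8 v 0 is needed (p = 0.0043 and 0.0046). The probability of eight or more cases in 60 children is about 3 in a million.

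**The case against.** The strongest reply is that nothing is broken. Bonferroni is valid, simple, and gives matching simultaneous confidence intervals, which may be worth more in a 60-child trial than a point or two of power. That stands, and it is why this is only a possible improvement.

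It is also fair to say that the larger gains depend on borrowing the primary outcome's 60% v 20% for outcomes such as hospitalization and imaging. The documents do not support those rates for them. Six real effects is an upper case too: section 2 says some detected pathogens need immediate therapy, so antibiotic use need not fall.

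A reader might infer three stronger points that the documents do not support:

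- **That the divisor is undefined, so the correction cannot be applied.** No number is written, but eight outcomes are numbered directly after the Bonferroni sentence, and that is the natural reading. Section 4.1.1 lists what will be tracked. The mismatch between the two lists is missing detail, not a fault in error control.
- **That HUS must come off the list because it wastes alpha.** Its test is close to hopeless, but at 30 per arm removing it leaves single-test power unchanged (59.9% at 0.05/8 and at 0.05/7 for 60% v 20%). HUS is also the disease that motivates the trial, so dropping its formal test is debatable.
- **That Holm beats Bonferroni whatever the list.** The guarantee is for one fixed list. With a smallest p-value of 0.0068, Bonferroni on seven rejects and Holm on eight does not.

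**Conclusion.** The point holds as a cheap improvement. On the eight outcomes in 4.4.2, Holm keeps the overall 0.05 and never rejects less than the planned correction. The benefit is nil if one effect is real, at most about 2 points of mean power with three, and up to about 7 points only if six large effects are real. These figures assume Fisher tests, 1:1 allocation and secondary rates that the documents do not give. The conclusion that Holm never does worse on the same list needs none of those assumptions.

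**What to change.** In 4.4.2, replace the Bonferroni correction with the Holm step-down procedure at an overall two-sided 0.05, applied to the eight outcomes numbered there: smallest p-value against 0.05/8, next against 0.05/7, and so on, stopping at the first non-rejection. State the number eight, name the test to be used for these outcomes, and fix the list before unblinded data are seen.

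Say that the other 4.1.1 outcomes (ED length of stay, renal replacement therapy, satisfaction) are outside this family unless added in advance. Satisfaction deserves an explicit decision, because Research Question 2 asks "Are patient and caregiver satisfaction higher in individuals randomized to testing with the BioFire FilmArray arm". Adding it would make nine outcomes and a first threshold of 0.05/9 = 0.00556.

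Optional and separate: report HUS as counts per arm with exact 95% intervals in place of a test, which fits Secondary Objective 1 ("To quantify clinical outcomes"). With no cases, the upper limit is 1 − 0.025^(1/30) = 11.6% for 30 children and 12.8% for 27. The list would then be seven, and the text should say so.

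The cost is a change of wording and the loss of simple simultaneous intervals that match the tests. No extra children are needed, and the primary analysis and sample size do not change.
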